**Section 11.3.9.2 (page 76)**

Current text: “Any death, SAE, pregnancy, or unexpected (and severe) AE experienced by the subject after informed consent through the last study visit, regardless of relationship to study drug, must be promptly reported (within 24 hours of the Investigator becoming aware of the event) by telephone or electronic transmission to the sponsor (or designee).”

Revised text: “Any death, SAE, or pregnancy, ~~or unexpected (and severe) AE~~ experienced by the subject after informed consent through the last study visit, regardless of relationship to study drug, must be promptly reported (within 24 hours of the Investigator becoming aware of the event) by telephone or electronic transmission to the sponsor (or designee).”

Rationale: To clarify, adverse (severe) events that are not considered SAEs do not need to be reported within 24 hours but reported per section 11.3.6.

Sincerely,

PPD

PPD

Syntimmune, Inc.

[name]

# SYNTIMMUNE

21-Sep-2017

**Protocol Number:** SYNT001-103  
**Protocol Name:** A Phase 1b, Multicenter, Open-Label, Safety, Tolerability, and Activity Study of SYNT001 in Subjects with Chronic Pemphigus (Vulgaris or Foliaceus)  
**IND Number:** 132727  
**Study Drug:** SYNT001  
**Protocol Version, Date:** 2.0, 12-April-2017  
**Clarification Letter Version:** 3.0  
**Subjects:** Inclusion Criteria

The purpose of this memo is to present a planned revision ahead of the next forthcoming protocol amendment. In the interim, please provide this correspondence to your Institutional Review Board as per local policy and request expedited review and approval.

## Section 5.2 Inclusion Criteria #5 (page 35)

Current Text: Body mass index (BMI) 18.5 – 35.0 kg/m^2

Revised text: Body mass index (BMI) 18.5 – 39.9 kg/m^2

Rationale: Patients who may be otherwise eligible to participate in the study are excluded due to BMI. We would like to be able to offer these individuals the opportunity to participate.

PPD

Syntimmune, Inc.

[name]

## PROCEDURES IN CASE OF EMERGENCY

### Serious Adverse Events

Any death or serious adverse event (SAE)\* occurring in a subject while receiving study drug or within 7 days of receiving study drug, even though the event may not appear to be study drug related, must be promptly reported (within 24 hours) by telephone or electronic communication to the sponsor (or designee).

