	
Exclusion criteria:
 
Subjects meeting any of the following criteria are to be excluded:
 
 
1. Subject unable or unwilling to comply with the protocol;
 
2. Active non-hematologic malignancy or history of non-hematologic malignancy in the 3 years prior to screening (exclusive of non-melanoma skin cancer and cervical cancer in situ);
 
3. Positive for HIV or hepatitis C antibody;
 
4. Positive for hepatitis B surface antigen;
 
5. Active infection or history of recurrent infections;
 
6. IVIG use within 60 days of screening;
 
7. Received any cytotoxic (other than azathioprine) or mAb therapy in the 3 months prior to screening;
 

	
8. Any exposure to an investigational drug or device within the 30 days prior to screening
 
9. Plasmapheresis or immunoadsorption within 60 days of screening
 
10. Cellular therapy, including CAR-T, at any time prior to screening
 
11. Use of any immunosuppressive drugs apart from corticosteroids, azathioprine, mycophenolate mofetil, or cyclosporine within 3 months of screening
 
12. Serum total IgG < 600 mg/dL;
 
13. Subject has any current medical condition that, in the opinion of the Investigator, may compromise their safety or compliance, preclude successful conduct of the study, or interfere with interpretation of the results (e.g., a significant pre-existing illness or other major comorbidity that the Investigator considers may confound the interpretation of the study results);
 
14. Any vaccination within 2 weeks of screening

Study drug, dosage, and administration
	
SYNT001
 
Doses: 10 mg/kg and 30 mg/kg. A third cohort of up to 8 subjects may be treated at another dose, with a maximum dose of 45 mg/kg, but may also be lower than 10 mg/kg or between 10 and 30 mg/kg, inclusive.
 
SYNT001 is provided as a liquid at a nominal concentration of 50 mg/mL. SYNT001 is diluted in Dextrose 5% in Water (D5W) to prepare the solution for infusion.
 
Route of administration: IV in 250 mL over 1 hour

Control, dose, and route of administration
	
Not applicable

Duration of subject participation and duration of study
	
Up to 126 days (18 weeks): Screening of up to 2 weeks (14 days); Treatment period of 8 weeks (56 days); Follow-up period of 8 weeks (56 days)

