### 7.18 Follow-up Day 112 (End-of-Study) or Early Termination Visit

On Day 112 ( $\pm$  5 days), subjects are to return to the clinic and the following procedures are to be performed:

- Complete physical exam ([Section 6.3](#))
- Vital sign measurements (after 5 minutes of rest; sitting blood pressure, heart rate, respiratory rate, oral temperature); abnormal results to be repeated after 5 minutes of rest ([Section 6.5](#))
- Clinical safety laboratory tests (hematology, serum chemistry panel, urinalysis) ([Section 6.7](#))
- Pregnancy test (Section 6.7)
- Serum tetanus antibody and VZV antibody testing if required. See [Section 6.7.3](#) for additional information.
- Immunogenicity sample collection (Section 6.7)
- PDAI Score ([Section 6.4](#))
- PD sample collection (Section 6.7)
  - IgG, IgG subtypes (IgG1-4), IgA, IgM
  - CIC
  - Anti-Dsg (1 and 3) antibody titer
  - C3
  - AECA
  - RNAseq
  - Urine IgG
  - Exploratory pemphigus immune response biomarkers
- Photography ([Section 6.11](#))
- Concomitant medication assessment ([Section 6.9](#))
- AE assessment ([Section 6.10](#))

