## **8.4 Stopping Rule**

### **8.4.1 Dose-Escalation Stopping Rule**

Dose escalation decisions will be made by a Dose Escalation Committee (DEC) and will be based on safety and pharmacodynamic evaluations including but not limited to, dose-limiting toxicities, AEs, SAEs, and total IgG levels.

Dose-limiting toxicity (DLT) will be defined generally as severe (Grade 3) AEs occurring in  $\geq 2$  subjects that are determined to be clinically significant and considered related to study drug.

If 2 or more subjects at any time in any cohort (8 total subjects per cohort) have Grade 3 AEs that are determined to be clinically significant and considered to be related to study drug, dosing will be halted within that cohort and dose-escalation to a higher dose will not occur. If the dose-escalation stopping rule is met during Cohort 1 (10 mg/kg) all safety data and all available pharmacodynamics will be reviewed and the cohort may resume (if applicable) or a new cohort may be added at a dose at least 50% lower than the 10 mg/kg dose. If the stopping rule is not met in Cohort 1, dose-escalation may proceed up to a maximum of 30 mg/kg. If the dose-escalation stopping rule is met for the first time during Cohort 2, all safety data and all available pharmacodynamics will be reviewed and the cohort may resume (if applicable) or a new cohort may be added at a dose a minimum of 30% lower than the Cohort 2 dose. If the stopping rule is not met in Cohort 2, dose-escalation may proceed up to a maximum of 45 mg/kg; however, this cohort may also receive a dose equal to or less than 30 mg/kg based on evaluation of all safety and pharmacodynamic data.

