### 9.3 Timing of Dosing

On Days 0, 7, 14, 21, and 28, subjects will receive a 60-minute IV infusion of SYNT001 in the morning. The date and time the dose is administered will be recorded.

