#### 11.3.1 Serious Adverse Events

*(Notify Medpace Safety within 24 hours; document on eCRF)*

The SAE definition and reporting requirements are in accordance with Title 21 Part Code of Federal Regulations (CFR) 312.32 and the Guidance for Industry and Investigators Safety Reporting Requirements for Investigational New Drug (INDs) and Bioavailability /Bioequivalence Studies.

SAE: An AE is considered "serious" if, in the view of either the Investigator or sponsor, it results in any of the following outcomes:

- **Death:** This includes any death that occurs while the subject is “on study” through the last study visit.
  - Note:** Death is an outcome of an AE, and not an AE. The event(s) that caused death (e.g., illness, accident) is the SAE. Death due to any other cause(s) must also be reported as an outcome of the reportable SAE.
- **Life-threatening adverse drug event:** An AE or suspected adverse reaction is considered “life threatening” if, in the view of either the Investigator or sponsor, its occurrence places the patient or subject at immediate risk of death. It does not include an AE or suspected adverse reaction that, had it occurred in a more severe form, might have caused death.
- **Inpatient hospitalization or prolongation of existing hospitalization:**

In the absence of an AE, the Investigator should not report hospitalization or prolongation of hospitalization. This is the case in the following situations:

  - Hospitalization or prolongation of hospitalization is needed for a procedure required by the protocol
  - Hospitalization or prolongation of hospitalization is part of routine procedure followed by study center

- Hospitalization for survey visits or annual physicals
- Hospitalization for observation with release within 24 hours

In addition, a hospitalization planned before the start of the study for a pre-existing condition, which has not worsened, does not count as an SAE.

- **Persistent or significant incapacity or substantial disruption of the ability to conduct normal life functions**
- **Congenital anomaly/birth defect**
- **Important medical event:** An event that may not result in death, be life threatening, or require hospitalization may be considered an SAE when, based upon appropriate medical judgment, it may jeopardize the subject and may require medical or surgical intervention to prevent one of the outcomes listed in this definition.

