**11.3.9.2 Time Frame for Reporting**

Any death, SAE or pregnancy experienced by the subject after informed consent through the last study visit, regardless of relationship to study drug, , must be promptly reported (within 24 hours of the Investigator becoming aware of the event) by telephone or electronic transmission to the sponsor (or designee).

Contact information for **SAE** reporting:

Medpace Clinical Safety  
Medpace SAE hotline:  
Telephone: PPD [redacted] dial P or PPD [redacted] dial P  
Facsimile: PPD [redacted] or PPD [redacted] D  
e-mail: PPD [redacted]

Additionally, the Investigator will be able to contact the **Medical Monitor**:

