### 11.3.9.3 Information to be Provided by the Investigator

SAEs must be recorded on the SAE form in the EDC system. This requirement includes all SAEs that occur after informed consent through the last study visit.

The minimum information required for SAE reporting includes identity of Investigator, site number, subject number, an event description, SAE term(s), onset date, the reason why the event is serious (i.e., the seriousness criteria) and the Investigator's assessment of the relationship of the event to study treatment. Additional SAE information including medications or other therapeutic measures used to treat the event, action taken with the study treatment due to the event, and the outcome/resolution of the event will be recorded. Paper forms for reporting SAEs will be provided to the study sites as back-up in case the EDC system is not accessible.

In all cases, the Investigator should continue to monitor the clinical situation and report all material facts relating to the progression or outcome of the SAE. Furthermore, the Investigator may be required to provide supplementary information as requested by Syntimmune or designee.

When reporting an SAE, the following additional points should be noted:

- When the diagnosis of an SAE is known or suspected, the Investigator should report the diagnosis or syndrome as the primary SAE term, rather than as signs or symptoms. Signs and symptoms may then be described in the event description. For example, dyspnea should not be used as an SAE term if the diagnosis, which caused the dyspnea, is known to be malignant pleural effusion.
- Death should not be reported as an SAE, but as an outcome of a specific SAE, unless the event preceding the death is unknown. In the exceptional case where the events leading to death are unknown, then death may be used as an event term. If an autopsy was performed, the autopsy report should be provided.
- While most hospitalizations necessitate reporting of an SAE, some hospitalizations do not require SAE reporting, as follows:
  - Elective or previously scheduled surgery, e.g., a previously scheduled ventral hernia repair
  - Procedures for pre-existing conditions that have not worsened after initiation of treatment
  - Pre-specified study hospitalizations for observation

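### The emergency page ties 24-hour SAE reporting to 7 days after a dose, while Section 11.3.9.2 runs it from consent to the last visit, so a site could notify the sponsor late

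*Protocol*

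**What the plan says.** Procedures in Case of Emergency, under Serious Adverse Events, requires prompt reporting (24 hours) to the sponsor or its designee of a death or SAE "occurring in a subject while receiving study drug or within 7 days of receiving study drug", even if the event does not seem drug related.

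Section 11 of the same version sets a longer period:

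- Section 11.3.9.2 applies the 24-hour duty to "Any death, SAE or pregnancy experienced by the subject after informed consent through the last study visit, regardless of relationship to study drug".
- Section 11.3.9.3, on the SAE form in the EDC system, states: "This requirement includes all SAEs that occur after informed consent through the last study visit".
- Section 11.3.1 carries the instruction "Notify Medpace Safety within 24 hours; document on eCRF" and gives no 7-day limit.

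On timing, Section 9.3 states: "On Days 0, 7, 14, 21, and 28, subjects will receive a 60-minute IV infusion of SYNT001". Section 7.18 is headed "Follow-up Day 112 (End-of-Study) or Early Termination Visit", so a subject who completes the study has the last visit on Day 112 (± 5 days).

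**The concern.** Two operative passages give different windows for the same duty, and no passage available for this review says which one prevails. The emergency page is the protocol's short reference for handling an SAE. Its own cross-reference is to Section 11.3.1 for the SAE criteria, not to Section 11.3.9.2 for the time frame.

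Safety is the primary objective, and three mechanisms benefit from prompt notice:

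- **Sponsor's report to the FDA.** Under Section 11.3.9.1 the limit of 15 calendar days runs from the sponsor's initial notification. If the site is late, the clock starts late.
- **Dose escalation committee.** It reviews drug-related SAEs over the course of the study (Sections 4.3 and 14.5) and must evaluate any related Grade 4 event before suspended dosing can go on (Section 8.4.2).
- **Escalation review.** The committee looks at data through Day 42 (Section 11.5), so Days 36 to 42 fall inside its review but outside the emergency-page window.

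The mismatch looks like a leftover. Follow-up was lengthened to Day 112 in version 2.0 and Section 11 now runs to the last visit, but the emergency page still has its 7 days. The clarification letter of August 2017 corrected the 24-hour rule in Section 11.3.9.2 and did not mention the emergency page.

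**Working it through.** The plan states no figure to reproduce here. The check is a comparison of texts and a day count.

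**Inputs.** Doses on Days 0, 7, 14, 21 and 28 (Section 9.3). Window of 7 days after a dose (emergency page). Screening from Day -14 (Section 7.1). Last visit Day 112 ± 5 days (Section 7.18). The synopsis total agrees: 14 + 56 + 56 = 126 days of participation, which is 127 calendar days from Day -14 to Day 112 counting both ends.

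**Emergency-page window, all five doses.** The doses are 7 days apart, so the windows join up. They run from Day 0 to 28 + 7 = Day 35, which is 36 calendar days.

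**What it leaves out of the Section 11.3.9.2 window.**

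- Before the first dose: Day -14 to Day -1 = 14 days.
- After Day 35: 112 - 35 = 77 days. The period after the last dose is 112 - 28 = 84 days, and 77/84 = 92%.
- In total: 14 + 77 = 91 of 127 days, or 72%.
- If the last visit falls at Day 117: 117 - 35 = 82 days after Day 35.

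**Subjects who stop dosing early.** Section 8.3 keeps them in follow-up through all scheduled visits. The window then closes 7 days after the last dose given:

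| Doses given | Window closes | Days left to Day 112 |
|---|---|---|
| 1 | Day 7 | 105 |
| 2 | Day 14 | 98 |
| 3 | Day 21 | 91 |
| 4 | Day 28 | 84 |
| 5 | Day 35 | 77 |

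**Can others still be on drug when the window closes?** Yes. Under Section 9.2 the second subject starts at least 24 hours after the first, and the remaining six wait for 7-day data on both. They start at the earliest on the first subject's Day 1 + 7 = Day 8, and their fifth infusion is due at the earliest on Day 8 + 28 = Day 36. That is the first day outside the first subject's window, and slower enrolment extends the overlap. Across cohorts, Cohort 2 may start once Cohort 1 data through Day 42 have been reviewed, when Cohort 1 subjects may have up to 112 - 42 = 70 days of follow-up left.

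**The case against.** The strongest reply is that the passages can both be obeyed. The emergency page says what must be reported. It does not say that only those events count, and it exempts nothing later. A site that follows Section 11.3.9.2 also satisfies the emergency page. Sections 11.3.1, 11.3.9.2 and 11.3.9.3 agree with each other, and the page's cross-reference leads to Section 11.3.1, which has no 7-day limit. That a site would open the emergency page first is an assumption. All this stands, and it limits the harm to a site that relies on that page alone. It does not remove the difference between the two stated windows.

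A reader might also infer three stronger points that the documents do not support:

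- **That late SAEs would escape the stopping rules.** They would not. Section 8.4.1 begins "If 2 or more subjects at any time in any cohort (8 total subjects per cohort) have Grade 3 AEs", and Section 8.4.2 covers any related Grade 4 event. Neither rule has a 7-day limit, and both turn on related graded AEs, not on the 24-hour notice. AEs are recorded on the eCRF (Section 11.2) and SAEs on the EDC form (Section 11.3.9.3) through the last visit.
- **That infections after the 7 days are the events of most interest.** No passage says so. Section 9.6.2 puts the single-dose IgG nadir at about 5 days. It expects return to within 30% of baseline within 4 weeks, from primate data for multiple doses, which is about Day 28 + 28 = Day 56. It adds that temporary depletion does not appear to raise infection risk. On those figures, reduced IgG outside the window would be expected over about Days 36 to 56 (21 days), not over all 77.
- **That 92% or 72% measures risk.** These are shares of calendar days. They include days after expected IgG recovery and, for the 72%, 14 screening days before any drug. They do not estimate how many SAEs would be reported late.

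**Conclusion.** The contradiction is real and stands between operative passages of the same version. With all five doses, the emergency page's 24-hour duty covers Day 0 to Day 35, whereas Section 11.3.9.2 covers consent to Day 112. The gap is the period before the first dose plus 77 of the 84 calendar days after the last dose, and it is longer for subjects who stop dosing early.

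The consequence is possible late notification to the sponsor. That would delay the 15-day FDA clock and the committee's review while other subjects may still be receiving drug. No event is lost, and no endpoint, analysis population or stopping criterion changes.

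This rests on three assumptions: that some site acts on the emergency page without going to Section 11.3.9.2; that consent is given at the start of the 14-day screening window, for the full count of 14 pre-dose days; and that the version compared, the latest in the part of the document available, is still in force. The emergency page was also not visible in full, because contact text had been removed.

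**What to change.** Reconcile the emergency page with Sections 11.3.9.2 and 11.3.9.3 so that one reporting window applies. The simplest way is to delete the window on the emergency page and cross-refer to Section 11.3.9.2. Repeating that section's window on the page would also work, but leaves two places to keep in step at the next amendment. Tell sites by memo in the meantime.

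The cost is one sentence in an administrative amendment and one memo. No data collection, analysis or visit schedule changes.

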### SAE CRITERIA

\* A serious adverse event (SAE) is any untoward medical occurrence that at any dose results in any of the following outcomes, regardless of relationship to study drug (see [Section 11.3.1](#), Serious Adverse Events for additional information):

- Death
- Life-threatening adverse drug event
- Inpatient hospitalization or prolongation of existing hospitalization
- A persistent or significant disability/ incapacity
- A congenital anomaly/birth defect
- An important medical event that may jeopardize the subject and may require medical or surgical intervention to prevent one of the outcomes listed above.

**1 SYNOPSIS**

Study title	A Phase 1b, Multicenter, Open-Label, Safety, Tolerability, and Activity Study of SYNT001 in Subjects with Chronic Pemphigus (Vulgaris or Foliaceus)
Protocol number	SYNT001-103
Number of study centers	Approximately 10 (US)
Clinical phase	Phase 1b
Study background	
SYNT001, a humanized, affinity-matured IgG4-kappa monoclonal antibody (mAb), blocks IgG and IgG immune complex (IC) interactions with the neonatal Fc receptor (FcRn) and thereby the major functions of FcRn in protecting IgG and IgG immune complexes from degradation and their role in downstream signaling events. Specific and high affinity blockade of FcRn with SYNT001 has been shown to increase the catabolism of IgG and IgG IC in healthy volunteers. This predicts that SYNT001 will also accelerate degradation of endogenous circulating IgG autoantibodies and IgG-antigen IC specifically involved in the pathogenesis of autoimmunity. Blocking FcRn interactions with IgG containing immune complexes further predicts that SYNT001 will have consequences for innate and adaptive cellular immunity. In the first instance, blocking multimeric IgG IC interactions with FcRn within antigen presenting cells will result in inhibition of IC-stimulated inflammatory cytokine production and release by these cells. In addition, as FcRn determines the intracellular itinerary of IgG immune complexes within and among compartments important in cellular immunity, it is further anticipated that SYNT001 will block antigen processing and presentation of antigens contained within IC that otherwise lead to CD8+ and CD4+ T cell activation. Thus, SYNT001 will specifically target immune functions associated with IgG and IC that are involved in many autoimmune conditions and dismantle their ability to cause disease.
 
SYNT001 targets mechanisms contributing to pathology in a variety of IgG-mediated autoimmune disorders, including warm antibody autoimmune hemolytic anemia (WAIHA), pemphigus, and chronic inflammatory demyelinating polyneuropathy (CIDP).
 
While current treatments for certain autoimmune disorders including chronic steroids, immunosuppressants, intravenous immunoglobulin (IVIG), plasmapheresis, and anti-CD20 monoclonal antibodies (mAbs), such as rituximab, can be effective, they are frequently associated with significant adverse effects, and delayed or non-durable responses.
 
Pemphigus is a rare group of blistering autoimmune diseases that affect the skin and mucous membranes. Autoantibodies are thought to play an important

	
pathogenic role in the mucosal and cutaneous manifestations in patients with pemphigus. Administration of SYNT001, leading to a significant decrease in total IgG, and thereby a corresponding decrease in the level of the pathogenic autoantibodies as well as the ICs to which they are associated, should lead to a decrease in the mucosal and cutaneous manifestations in subjects with pemphigus. Moreover, the ability of SYNT001 to reduce circulating immune complexes (CICs) and the associated innate and adaptive immune responses may allow for further sustained disease modification.

Study rationale
	
This study is being conducted to further evaluate the safety, tolerability, pharmacokinetics (PK), pharmacodynamics (PD) and immunogenicity of intravenous (IV) SYNT001 as well as its effects on pemphigus disease activity markers.

Study objectives
	
Primary objective
 
 
• To evaluate the safety and tolerability of 5 once-weekly IV infusions of SYNT001 at different dose levels in subjects with chronic pemphigus (vulgaris or foliaceus)
 
 
Secondary objectives
 
 
• To determine the PK of SYNT001 following 5 once-weekly 1-hour IV infusions at different dose levels
 
• To assess the effect of 5 once-weekly doses of SYNT001 at different dose levels on the following PD biomarkers: 
 
○ Immunoglobulins: IgG, IgG subtypes (IgG1-4), IgA, IgM
 
○ Albumin
 
 
 
• To assess the effect of 5 once-weekly doses of SYNT001 at different dose levels on the following disease activity markers: 
 
○ Serum anti-desmoglein (Dsg) (1 and 3) antibody levels
 
○ Pemphigus Disease Area Index (PDAI)
 
 
 
• To assess immunogenicity (anti-SYNT001 antibodies)
 
 
Exploratory objectives
 
 
• To assess the effect of 5 once-weekly doses of SYNT001 at different dose levels on the following biomarkers, including: 
 
○ Serum anti-epithelial cell antibody (AECA) levels by indirect immunofluorescence
 
○ Circulating immune complexes (CIC)
 
○ Complement component 3 (C3)
 
○ Exploratory biomarkers (FCGR2A (single nucleotide polymorphism-SNP), RNAseq, urine IgG)
 
 
 

	
 
○ Immune phenotyping by flow cytometry for CD3+CD4+ T, CD3+CD8+ T, monocytes, NK cells and B cells
 
○ SYNT001 levels in skin biopsies (optional)
 
○ Exploratory biomarkers to investigate immune response associated with pemphigus
 
 
 
● To characterize corticosteroid use during the study
 
									
Study design	Phase 1b, multicenter, open-label, safety, tolerability, and activity study									
Methodology	
Two cohorts of 8 eligible subjects each will receive 5 once-weekly 60-minute infusions of SYNT001 in planned doses of 10 mg/kg or 30 mg/kg. Based on review of safety, PD, and clinical outcomes of these 2 cohorts, a third cohort of up to 8 subjects may be treated at another dose, with a maximum dose of 45 mg/kg, but may also be lower than 10 mg/kg or between 10 and 30 mg/kg, inclusive.
 
  
 Cohort	No. of subjects	Dose	
   
 1	8	SYNT001 10 mg/kg	
 
 2	8	SYNT001 30 mg/kg	
  
 
Cohorts will be dosed sequentially beginning with Cohort 1. The first 2 subjects will be dosed at least 24 hours apart. A review of the 24-hour safety data for the first subject will be performed to ensure that there are no overt safety concerns before dosing the second subject. A review of the 7-day safety data for the first 2 subjects will be performed prior to dosing the remaining 6 subjects in the cohort. This evaluation will include a review of AE/SAE reports, vital sign assessments, physical examinations, ECGs, and clinical laboratory testing. The seriousness, severity, and relatedness of AEs/SAEs will also be considered in the safety evaluation. Safety data will be reviewed on a continuous basis throughout the study. All safety data and any available and relevant PD data through Day 42 (2 weeks after the last subject's last dose in Cohort 1) will be reviewed by a dose escalation committee before Cohort 2 is initiated. Escalation to Cohort 2 will proceed if there are no concerning safety signals and the review of available and relevant PD data supports advancing to a higher dose. The dose for Cohort 2 will be finalized after review of the safety and PD data, but will not exceed 30 mg/kg. Cohort 2 and Cohort 3, if added, will be dosed per the same schedule as Cohort 1.
 
On days where study drug is administered, vital sign and pulse oximetry measurements will be collected immediately prior to the infusion; 15, 30, and 45 minutes after the start of the infusion; at completion of the infusion; and 30 minutes, 1 hour and 2 hours following completion of the infusion.
 
On Days 0 and 28, PK blood samples will be collected prior to infusion start and then over the subsequent 48 hours. Subjects will remain at the clinic through the
	Cohort	No. of subjects	Dose	1	8	SYNT001 10 mg/kg	2	8	SYNT001 30 mg/kg
Cohort	No. of subjects	Dose								
1	8	SYNT001 10 mg/kg								
2	8	SYNT001 30 mg/kg								

	
6-hour PK sample collection and will return to the clinic for the 24- and 48-hour collections. Additional samples will be collected on Days 5 and 33.
 
On Day 0 photographs will be taken of active lesions. Follow-up photographs will be taken of the same areas on Days 33, 56, 84 and 112. If a subject begins a steroid taper, additional photographs will be taken at the clinic visit during which the decision to begin the taper is made.
 
Subsequent visits will occur on Days 1, 2, 5, 7, 12, 14, 19, 21, 28, 29, 30, 33, 42 and 56 for safety assessments, study drug dosing, sample collections, and other study procedures.
 
Subjects will return to the clinic on Days 84 and 112 for follow-up visits. Subjects whose total IgG is not within 30% of their Day 0 baseline value and not above 500 mg/dL at the Day 112 visit will be referred for further management.
 
See Table 1 for a schedule of all study events. To assess safety and tolerability, subjects will undergo physical examinations (PEs; including weight), vital sign measurements, clinical (safety) laboratory tests, adverse event (AE) assessments, concomitant medication assessments, and electrocardiograms (ECG).

Number of subjects
	
Approximately 16; two cohorts of 8 subjects each. An additional cohort of up to 8 subjects may be enrolled. Subjects who withdraw for any reason other than an AE and who do not receive study drug or have only received one dose of study drug may be replaced, up to one subject per cohort. The maximum number of subjects who may be enrolled in this study is 27 (24 + up to 3 replacements, as necessary). Within each dosing cohort, no more than 3 subjects with pemphigus foliaceus may be enrolled.


Diagnosis and main entry criteria
	
Inclusion criteria:
 
Subjects must meet the following criteria to be included:
 
 
1. Willing and able to read, understand and sign an informed consent form;
 
2. Male or female <math>\geq</math> 18 years of age at the time of screening;
 
3. Documented diagnosis of pemphigus vulgaris or foliaceus based on all 3 of the following criteria:             
 
a. Documented clinical history consistent with pemphigus vulgaris or foliaceus (clinical presentation defined as mucosal and/ or skin lesions);
 
b. Presence of Anti-Dsg 1 or 3 antibodies above the upper limit of normal;
 
c. History of at least one positive tissue-based test (e.g., biopsy, direct immunofluorescence [DIF])
 
 
 
4. Active disease: Lesions lasting <math>></math> 2 weeks, and 3 active lesions in skin or mucosa or 2 active lesions with at least one being a skin lesion <math>></math> 1 cm diameter:
 

	
 
a. If treated with rituximab or other anti-CD20 antibodies, last dose > 12 months prior to screening;
 
b. If being treated with other immunosuppressants (i.e., azathioprine, mycophenolate mofetil or cyclosporine), must be on stable dose (< 10% change in dose) for 6 weeks prior to screening;
 
c. If being treated with corticosteroids, must be ≤ 1mg/kg/day of prednisone or equivalent and stable (< 10% change in dose) for 2 weeks prior to screening;
 
d. Allowed topical therapies for pemphigus lesions upon entering the study include petroleum jelly or Aquaphor® for the skin or chlorhexidine for the mouth
 
 
 
5. Body mass index (BMI) 18.5 – 39.0 kg/m^2;
 
6. Has a negative pregnancy test (for women of childbearing potential) documented prior to the first dose of study drug;
 
7. Females of childbearing potential must agree to be abstinent or else use any two of the following medically acceptable forms of contraception (<1% per year failure rate) from the Screening Period through the final study visit: oral contraceptive, condom with or without spermicidal jelly, diaphragm or cervical cap with spermicidal jelly, or intra-uterine device (IUD). A female whose male partner has had a vasectomy must agree to use one additional form of medically acceptable contraception.
 
8. Females of non-childbearing potential, defined as surgically sterile (status post hysterectomy, bilateral oophorectomy, or bilateral tubal ligation) or post-menopausal for at least 12 months do not require contraception during the study.
 
9. Males with female partners of childbearing potential, including males who are surgically sterile (post vasectomy), must agree to be abstinent or else use a medically acceptable form of contraception from the screening period through the final study visit.
 

	
Exclusion criteria:
 
Subjects meeting any of the following criteria are to be excluded:
 
 
1. Subject unable or unwilling to comply with the protocol;
 
2. Active non-hematologic malignancy or history of non-hematologic malignancy in the 3 years prior to screening (exclusive of non-melanoma skin cancer and cervical cancer in situ);
 
3. Positive for HIV or hepatitis C antibody;
 
4. Positive for hepatitis B surface antigen;
 
5. Active infection or history of recurrent infections;
 
6. IVIG use within 60 days of screening;
 
7. Received any cytotoxic (other than azathioprine) or mAb therapy in the 3 months prior to screening;
 

	
8. Any exposure to an investigational drug or device within the 30 days prior to screening
 
9. Plasmapheresis or immunoadsorption within 60 days of screening
 
10. Cellular therapy, including CAR-T, at any time prior to screening
 
11. Use of any immunosuppressive drugs apart from corticosteroids, azathioprine, mycophenolate mofetil, or cyclosporine within 3 months of screening
 
12. Serum total IgG < 600 mg/dL;
 
13. Subject has any current medical condition that, in the opinion of the Investigator, may compromise their safety or compliance, preclude successful conduct of the study, or interfere with interpretation of the results (e.g., a significant pre-existing illness or other major comorbidity that the Investigator considers may confound the interpretation of the study results);
 
14. Any vaccination within 2 weeks of screening

Study drug, dosage, and administration
	
SYNT001
 
Doses: 10 mg/kg and 30 mg/kg. A third cohort of up to 8 subjects may be treated at another dose, with a maximum dose of 45 mg/kg, but may also be lower than 10 mg/kg or between 10 and 30 mg/kg, inclusive.
 
SYNT001 is provided as a liquid at a nominal concentration of 50 mg/mL. SYNT001 is diluted in Dextrose 5% in Water (D5W) to prepare the solution for infusion.
 
Route of administration: IV in 250 mL over 1 hour

Control, dose, and route of administration
	
Not applicable

Duration of subject participation and duration of study
	
Up to 126 days (18 weeks): Screening of up to 2 weeks (14 days); Treatment period of 8 weeks (56 days); Follow-up period of 8 weeks (56 days)


Prohibited Concomitant treatments
	
All treatments a subject receives within 14 days prior to enrollment through the end of the study will be documented. Concomitant medication and treatment for co-existing conditions, including those for pemphigus, are permitted if not excluded below. Topical antibiotics are permitted to treat active infections that occur on study. Topical or systemic treatments for oral candidiasis are permitted. Topical lidocaine for transient pain relief is acceptable as needed. Significant increases in anti-pemphigus medications will result in subjects being discontinued from the study. Concomitant treatment that is medically indicated for any AEs the subject experiences during the study are permitted. Premedication is discouraged as prophylaxis against AEs or infusion reactions unless medically indicated from either past medical history, prior infusion reactions or AEs resulting from SYNT001 infusions.
 
Use of the following medications will not be permitted during the study unless otherwise specified:
 
 
• Rituximab or other anti-CD20 antibody
 
• Monoclonal antibodies other than study drug
 
• Any immunosuppressive drugs apart from corticosteroids, azathioprine, mycophenolate mofetil, or cyclosporine
 
• Topical steroids
 
• Any dietary herbal supplements
 
• Any investigational drug or device
 
• Any vaccinations through Day 56. Following Day 56, subjects may receive vaccinations at the discretion of the Investigator.
 
 
If over a period of at least two weeks on study drug, a subject on corticosteroids shows the absence of new lesions and significant healing of lesions that existed at study baseline, a slow corticosteroid taper may be started as per the following suggested schedule
 
 
• If on > 30 mg of prednisone per day, decrease by 10 mg every two weeks until a dose of 30 mg per day then decrease by 5 mg every two weeks
 
• If on < 30 mg of prednisone per day, decrease by 5 mg every two weeks
 


Safety assessments
	
Safety assessments include AEs, serious adverse events (SAEs), PEs, vital sign measurements, clinical safety laboratory evaluations, ECGs, and reasons for treatment discontinuations due to toxicity. Safety assessments will be performed at specified time points and prior to discharge from the clinic. Vital sign measurements, including blood pressure, pulse rate, respiratory rate, and temperature will be monitored throughout the study. Pulse oximetry will be monitored during the study drug infusion and for 2 hours following the end of the infusion.

	
The National Cancer Institute Common Terminology Criteria for Adverse Events (NCI CTCAE; Version 4.03) will be used for grading clinical and laboratory AEs.
 
The AE reporting period for a subject enrolled in the study begins when the subject provides informed consent and is continued through the last study visit. All AEs that occur in the enrolled subjects during the AE reporting period must be recorded, regardless of the relationship of the AE to study drug. Any known untoward event that occurs beyond the AE reporting period that the Investigator assesses as related to study drug should also be recorded.

